12.1 Periodic Reports to the Sponsor/Monitoring

Periodic reports will be given to the sponsor in line with the frequently held monitoring visits.

The activities/reporting by the monitor that take place during the on-site visit include, but are not limited to the following:

- Only subjects who meet the study eligibility criteria are enrolled
- Informed consent process was conducted appropriately and that informed consent will be obtained prior to proceeding with any study procedures
- Data was collected and analysed as specified in the protocol
- Adverse events were reviewed promptly and reported as required
- Privacy and confidentiality of subjects was maintained
- Documentation of dropouts
- Evaluation of primary and secondary endpoints
- During an annual visit, the Monitor focuses on the areas where the majority of the deficiencies were identified or addresses other problems or issues noted since the last visit.
- The Monitor identifies and reports any suspected fraud and scientific misconduct if discovered during the review.

The clinical monitoring process of the sponsor can be classified into the following periodical visits:

12.1.1 Study initiation visit

The monitor conducts the study initiation visit after the site submits the protocol to its IRB and in advance of study activation.

The study initiation visit is held at the study site. The monitor prepares a clinical study initiation visit report to document the study initiation visit. The PIs, Sub-Investigators, and Site Coordinators must be prepared to discuss the procedural as well as the scientific aspects of the protocol during the initiation visit.

12.1.2 Annual Monitoring Visit

The monitor schedules and conducts on-site monitoring visits. The first annual monitoring visit to the study site occurs 12 months after a study opens; then annually thereafter until study closure.

The monitor may conduct interim visits as requested. An interim visit can be conducted as a follow-up to an annual visit where a number of deficiencies were identified, or it can be requested for reasons such as the complexity of the study, staff changes, or number of subjects enrolled.

The annual visit is generally scheduled for two days. The monitor prepares a follow-up-monitoring report to document the visit.

12.1.3 Close-Out Visit

The monitor schedules the close-out visit. The close-out visit usually takes one full day. If accrual is exceptionally large, an additional day can be required.

The activities/assessments by the monitor during the close-out visit include, but are not limited to, the following:

- Complete any outstanding site monitoring tasks (e.g., regulatory review and/or review of participant records) through the date of study termination or completion;
- Confirm that the IRB has been informed of the study closure
- Ensure the PI understands follow-up requirements for reporting AEs for subjects who have completed the study
- Conduct a summary meeting with Study Principals to discuss findings and plans for resolution of outstanding issues

A final report will be prepared after finishing all monitoring activities.

13 Changes of the Clinical Investigation Plan

13.1 Amendments to the CIP

All amendments to the CIP shall be agreed to by the principal clinical investigator and be recorded with a justification for the amendments. Deviations will be reviewed to determine the need to amend the CIP or to terminate the investigation.

14 Deviations from the Clinical Investigation Plan (CIP)

14.1 Deviations from the Clinical Investigation Plan

Any deviation from the CIP will be documented together with an explanation for the deviation. Deviations will be reported to principal investigator who is responsible for analyzing the deviations and assessing their significance.

Other Reportable Information and Occurrences (ORIOs: such as protocol deviations, accidents/incidents, and complaints) will be reported to IRB in the form of an ORIO report:

- Within 7 days when urgent subjects safety or regulatory concerns exist and/or oversight letter is received
- Within 15 days when situations or event potentially alters risk-benefit assessment and/or may jeopardize integrity of study results and/or potential benefits to subjects
- With scheduled continuation review or concurrently with report to oversight body, whichever comes first, when ORIO falls outside of other IRB timeframe parameters

14.2 Withdrawal / Dropout of Subjects

Table 14.1.2 Withdrawal and drop-out of subjects separated by level, reason and consequences

Level	Cause	Consequence
Lesion	An allocated lesion progresses radiographically into the middle or inner 1/3 of dentin (criteria D2 and D3).	
The lesion is treated invasively by removing the caries and placing a filling.
 
The case is scored as "progressed" and "failure".

	The patient shows signs of reversible or irreversible pulpitis in an allocated tooth.	
The tooth is treated.
 
The case is scored as "progressed" and "failure".

Patient	The patient shows adverse reactions for one of the study materials.	
Counteractive measures are taken.
 
Unwanted effects are documented in CRF and CEF.
 
The patient is scored as "drop out", data will be assigned as "last observation carried

		forward".
	The patient can not be examined (i.e. x-ray during pregnancy)	The patient is scored as "drop out", data will be assigned as "last observation carried forward".
	One or more allocated lesions have been treated by an external dentist.	The patient is scored as "drop out", will be assigned as "last observation carried forward".
	The patient can not be contacted to make appointments.	The patient is scored as "drop out".
	The patient decides to withdraw his informed consent or study participation.	The patient is scored as "drop out".
Study	One or more patient(s) show severe unwanted side effects to treatment.	Individual counteractive measures are taken. The study is halted.
	More than five patients show unwanted side effects to one treatment or material used.	Individual counteractive measures are taken. The study is halted.

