8.2 Clinic visits

A trained study clinician will perform all standard clinical assessments of study lesions in groups 1 and 2, including visual exam and radiograph exam. The study clinician will provide Icon treatment to all study participants randomized to study arm 1 after the radiograph and visual exam. The study clinician will provide oral hygiene instruction and topical fluoridation therapy (Duraphat fluoride varnish) to all study participants randomized to study arm 2 after the radiograph and visual exam.

A trained study clinician will capture the SFE laser optical device image of the study lesions from all study participants. The study examiner will be trained and calibrated by the HPL research team prior to start of study. SFE laser optical device image diagnoses from baseline will be compared to diagnoses from radiograph and visual exams from chart review from the same visit.

Table 8.2 Overview of the procedures during each visit

Procedure	Screening visit	Baseline and Intervention	12 Month Follow-up	24 Month Follow-up
Time		D-0	M 12 (± 3 m)	M 24 (± 3 m)
Patient information	x			
Oral examination	x		x	x
Informed consent	x			
Medical history	x			
Inclusion and exclusion criteria	x		x	x
Selection of eligible lesions	x			
Caries risk assessment	x			
Placing ortho spacers(tx group) D-21 to -7 prior to BI		x	x	x
Randomization	x			
Radiographic examination		x	x	x
Examination by SFE Before spacers placed	(x)*	x		
Examination by SFE Before & After Icon placed		x	x	x
Examination by SFE		x		
Visual Assessment of lesion		x	x	x
Intervention (Infiltration) (EXPERIMENTAL)		x		
Instruction for oral health care		x	x	x
Record of adverse effects		x	x	x
Fluoridation (CONTROL)		x	x	x

*Can be done at screening or baseline appointment

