11.4 Statistical Analysis

11.4.1 Descriptive Statistics

Descriptive statistics (means, standard deviations, counts, and percentages) will be calculated for all variables. A Chi-square test of association will be performed to evaluate if there is a significant difference in caries arrest by treatment group at a significance level of 0.05. Additional Chi-square tests of association will be performed to determine if there is a significant association with the secondary outcomes by treatment group.

11.4.2 **Blinding**

Each subject enrolled into this study will be assigned a unique identifying code number. Every effort will be made to maintain the confidentiality of each study subject's identity. No presentation or publication of the study data will identify any study subject.

11.4.3 **Evaluation of Records**

SFE laser optical device image diagnoses from each time point will be compared to diagnoses from radiograph and visual exams from chart review from the same visit.

- For radiograph and visual exams: Assessments of caries lesions per standard of care will be abstracted from the electronic dental record system (Axium) and recorded on CRF.
- For SFE laser optical device image: Recordings from the device will be used to assess caries lesions and recorded on CRF.

11.4.4 **Missing Data**

Missing data due to dropouts have been accounted for in adjusted sample size. The missing data will be at random. Data of dropouts will be assigned as "last observation carried forward".

11.4.5 **Statistical Software**

STATA Data Analysis and Statistical Software will be utilized to perform data analysis.

12 Method of Reporting

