18.1 Adverse Events

An adverse event (AE) is defined as any unintended adverse experience associated with the study materials or study procedures that results in an unplanned medical assessment or treatment, or changes the risk to subjects. Any adverse reaction to the treatment provided as part of the study will be fully investigated and reported to the IRB. AEs will be reported according to the IRB defined timelines using appropriate forms.

All materials and devices used in this study have been approved by local regulatory bodies and are currently on the market in various parts of the world. Their clinical use is according to label. Therefore, no foreseeable adverse events are expected.

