18.2 Serious Adverse Events

Emergency contact details for reporting of serious adverse events are included in the CIP (Appendix A5).

Serious Adverse Events are adverse events that:

- a) led to a death,
- b) led to a serious deterioration in health that either:
 - 1) resulted in a life-threatening illness or injury, or
 - 2) resulted in a permanent impairment of a body structure or a body function, or
 - 3) required in-patient hospitalization or prolongation of existing hospitalization, or
 - 4) resulted in medical or surgical intervention to prevent life threatening illness or injury or permanent impairment to a body structure or a body function.
- c) led to fetal distress, fetal death or a congenital abnormality or birth defect.

In case of a serious adverse event and subsequent need for un-blinding the name-code list can be assessed immediately and breaking the code will not cause any further problem. The data recorded until the report of adverse event will remain included in the dataset.

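### Table 14.1.2 makes any child who reacts to a study material a drop-out with last observation carried forward, which can score an unobserved lesion as not progressed and leaves later safety recording unprovided for

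*Combined protocol and SAP*

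**What the plan says.** Protocol 14.2, Table 14.1.2, gives as a patient-level cause: "The patient shows adverse reactions for one of the study materials". Three consequences follow. Counteractive measures are taken. "Unwanted effects are documented in CRF and CEF". Then: "The patient is scored as 'drop out', data will be assigned as 'last observation carried" (the sentence ends with the word forward). No grade of severity is attached.

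Protocol 11.4.4 applies the same imputation generally: "Data of dropouts will be assigned as 'last observation carried forward". It also asserts that missing data will be at random.

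Protocol 18.1 says: "Any adverse reaction to the treatment provided as part of the study will be fully investigated and reported to the IRB". It gives no duration, visit or end point for that investigation. Protocol 18.2, under serious events and next to the unblinding provision, says: "The data recorded until the report of adverse event will remain included in the dataset". It does not mention data recorded later.

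In Table 8.2 the row "Intervention (Infiltration) (EXPERIMENTAL") is marked at the baseline and intervention visit only. Control fluoridation is marked at baseline, month 12 and month 24, and so is the recording of adverse effects. A further row of Table 14.1.2 halts the study when: "More than five patients show unwanted side effects to one treatment or material used".

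**The concern.** The rule treats a reaction to a material as a reason to stop observing the child. For Icon no further application is scheduled, so the exit removes only observation: the two remaining adverse-effect records, examinations and radiographs. Section 18.1 promises a full investigation, but the only scheduled visits at which the course of a reaction would be recorded are the ones a drop-out leaves.

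The second problem is the value put in place of the missing outcome. Lesions enter at E1 or E2. If the reaction occurs at the only Icon visit, the last observation is the baseline, and a lesion equal to its own baseline has not progressed. A child who reacts to Icon then adds an Icon success to the 2-year primary outcome, whatever happens to the tooth. An exit triggered by the treatment received cannot be presumed to be at random, as 11.4.4 asserts.

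The exit is also by patient, while 9.3 allocates lesions and up to two per child may be enrolled. An unaffected second lesion, possibly in the other arm, leaves with the first.

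**Working it through.** No figure in the plan is at issue, so the check has two parts: the text, then an illustration of size.

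**Text**

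1. Trigger and consequence (Table 14.1.2): any reaction to any study material leads to drop-out with LOCF.
2. Exposure still to come (Table 8.2): none for Icon after baseline. For varnish, applications are marked at months 12 and 24.
3. Observation still to come (Table 8.2, section 9.5): adverse-effect record, visual examination and radiograph at months 12 and 24. No section says that a drop-out attends these.
4. Carried value: section 7.2.1 and the note to Figure 3 restrict entry to E1 and E2. A reaction at baseline carries that reading, hence not progressed. A reaction at month 12 would carry the month-12 reading.

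**Size: inputs and assumptions**

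- 25 lesions per arm (9.3); primary outcome is the proportion progressed at 2 years, compared by Fisher's exact test (SAP).
- Progression of 23% with infiltration and 62% with control, the 1-year primary-tooth figures cited in the SAP. The SAP gives no 2-year proportions for each arm, so using these is an assumption.
- Two-sided test at 0.05. The SAP does not state sidedness, so this too is assumed.
- Lesions are treated as independent, reactions occur at baseline, and all other lesions are observed.
- k = number of lesions carried forward. The reaction rate is not given (4.3.3 says only that incidence is low), so a range is shown. The halt rule tolerates up to five patients per treatment or material. With one lesion each, that is k = 5.

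**Formulas**

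Expected progression in an arm with k lesions carried: (25 − k) × p / 25.

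Probability of rejection with k Icon lesions carried: sum over a and b of Bin(a; 25 − k, p_Icon) × Bin(b; 25, p_control), taken over tables with Fisher p ≤ 0.05.

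**No true effect, 62% in both arms, k Icon lesions carried**

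| k | Expected Icon progression | False benefit (0.62 × k / 25) | Rejection rate |
|---|---|---|---|
| 0 | 62.0% | 0 | 2.8% |
| 1 | 24 × 0.62 / 25 = 59.5% | 2.5 points | 2.9% |
| 3 | 22 × 0.62 / 25 = 54.6% | 7.4 points | 4.7% |
| 5 | 20 × 0.62 / 25 = 49.6% | 12.4 points | 8.8% |

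**True effect, 23% against 62%**

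With nothing carried, the difference is 39 points and power is 76.1%.

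| k | Icon lesions carried: difference, power | Control lesions carried: difference, power |
|---|---|---|
| 1 | 39.9 points, 78.4% | 36.5 points, 70.1% |
| 3 | 41.8 points, 82.7% | 31.6 points, 55.9% |
| 5 | 43.6 points, 86.6% | 26.6 points, 40.0% |

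The direction therefore depends on which material causes the reaction. Per lesion carried, the distortion under a true effect is larger on the control side, because more control lesions would have progressed.

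**The case against.** The strongest reply is that the plan does not abandon these children. Table 14.1.2 requires counteractive measures and documentation, and 18.1 requires investigation of every reaction. Section 18.4 provides for updates on reportable events, and 12.1.3 mentions adverse-event reporting for subjects who have completed the study. This stands. A reader might infer that all safety follow-up ends on the day of the reaction, but no section says so. What is missing is any provision that the scheduled recording continues.

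Other tempting readings also fail:

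- That the outcome is lost. The observed outcome is lost, but LOCF supplies a value, and that value is the route to bias.
- That 18.2 discards later data. Its sentence guarantees that earlier data stay in, concerns serious events, and is silent on what follows.
- That nothing remains to be stopped after any reaction. This is true of Icon only, since varnish is marked at three visits.
- That every harmed child is affected. Table 14.1.2 scores pulpitis in a study tooth as progression and failure, not as drop-out.
- That five reacting children use up the SAP's attrition allowance. Five of 25 is 20% of one arm, but the allowance covers the whole trial (50 − 42 = 8 lesions), and 5/50 is 10%. Under LOCF these lesions also stay in the denominator.

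Finally, reactions are expected to be rare: 4.3.3 reports a low incidence, 18.1 foresees no adverse events, and 7.2.2 excludes children with a documented reaction to such materials. This limits the size of the bias but does not change its direction.

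**Conclusion.** The point holds as a stated rule with a bias of known direction, together with a gap in provision for safety recording. Followed as written, a baseline reaction to Icon places a lesion in the primary outcome as not progressed without anyone having looked at it again. A baseline reaction to varnish does the same for control.

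The numerical effect is probably small. One Icon lesion carried forward moves the null rejection rate from 2.8% to 2.9%, and three still leave it below 5%. It takes five, the most the halt rule allows with one lesion per child, to reach 8.8%. That is an upper illustration under the plan's own limit and not an expected rate. A more extreme case, five children each with two Icon lesions (k = 10), gives 33.7%, but nothing in the documents makes it likely. All these figures rest on reactions at baseline, independent lesions, and the cited 1-year proportions.

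The gap in scheduled safety recording does not depend on the reaction rate: it applies to each child who reacts and still has visits to come.

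**What to change.** In the adverse-reaction row of Table 14.1.2, replace the drop-out and LOCF consequence with a statement that:

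- an adverse reaction does not by itself end observation;
- unless consent is withdrawn, the scheduled month-12 and month-24 adverse-effect record, examination and standard-of-care radiograph are still collected and analysed in the allocated arm, for every enrolled lesion of that child;
- LOCF does not replace an outcome that can be observed.

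In 18.2, add that data recorded after the event are also kept, and require that the course and outcome of the reaction be recorded. The report form (Appendix A6) was not available here and may already have space for this. Reconcile 14.2, 18.1 and 18.2 so that they describe one process. Decisions on further exposure to any material lie outside this change.

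The cost is wording in two sections and a few more follow-up records for affected children. The visits are already scheduled, and section 8.1 says the radiographs are taken as standard of care.

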14.3 Length of follow-up – Potential Study Extension

Based on the actual study design there is no extension planned. If obtained data indicate a necessity for follow-up investigations this issue will be discussed with the sponsor and documented in the study files.

15 Confirmation of Study Material Application

Application of study material will be documented in the Study Material Application form (Appendix A2) including patient ID, investigator, date of application, material batch number and signature.

16 Ethical Considerations

This protocol was approved by the ethical committee from the Center for Pediatric Dentistry, Seattle, Washington (Appendix A3). Parents or guardians will sign an informed consent. (Appendix A4). Operative dental treatment will be provided to the participants when necessary.

17 Relevant Standards and Guidelines

The Clinical Investigation Protocol for this study includes all components and documentation as required to conform to international standards for clinical research (CONSORT⁴⁶, ISO/DIN⁴⁷ and Good Clinical Practice Guidelines⁴⁸).

18 Adverse Events

18.1 Adverse Events

An adverse event (AE) is defined as any unintended adverse experience associated with the study materials or study procedures that results in an unplanned medical assessment or treatment, or changes the risk to subjects. Any adverse reaction to the treatment provided as part of the study will be fully investigated and reported to the IRB. AEs will be reported according to the IRB defined timelines using appropriate forms.

All materials and devices used in this study have been approved by local regulatory bodies and are currently on the market in various parts of the world. Their clinical use is according to label. Therefore, no foreseeable adverse events are expected.

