1.4 Abstract

Introduction: Research efforts using Icon have been in regard to its efficacy on treating early caries and white spot lesions. It has been found by numerous studies to be an effective form of treatment on stopping caries before traditional restorative work needs to take place. [REDACTED]

[REDACTED]

[REDACTED]

[REDACTED]

[REDACTED]

Objective: The hypothesis to be tested is that Icon performs similarly to an established prevention strategy for early caries (Oral hygiene instruction and topical fluoridation) for caries arrest; and caries progression may be imaged through a SFE laser optical device.

Materials and Methods: We propose a [REDACTED] study of Icon vs. control (Oral Hygiene Instructions [OHI]) and topical fluoridation) for early caries arrest in primary molars. Lesion depth will be performed through standard-of care methods, i.e. radiographs and visual exams, plus a novel optical device based on scanning fiber endoscope (SFE) technology for laser light imaging for early caries detection in pediatric populations. We will utilize SFE laser optical device prototypes developed by the University of Washington's Human Photonics Lab (HPL), a device already in human use for other applications, including imaging and cancer screening.

Clinical Significance: This controlled trial will assess the positive effects of [REDACTED] infiltration by ICON and may open a new therapeutic strategy in pediatric dentistry. Additionally, this study would be one of the first in vivo dental applications of the SFE optical device, and would add a novel early caries visualization technique to the armamentarium for detecting caries progression.

2 Description and Properties of the Medical Device to be investigated

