18.3 Report by the investigator to the sponsor

DMG has implemented and maintains a system to ensure that the reporting of the reportable events will be provided by the investigator to the sponsor in acceptable timely conditions using the Adverse Event/ Adverse Device Effect (AE/ADE) Report Form (Appendix A6).

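### The adverse event definition is conditional on association with the study and serious events inherit that condition, so events considered unrelated fall outside AE/SAE recording and reporting

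*Combined protocol and SAP*

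**What the plan says.** Section 18.1 defines an adverse event as "any unintended adverse experience associated with the study materials or study procedures that results in an unplanned medical assessment or treatment", and adds a second qualifying consequence, "or changes the risk to subjects". On reporting it says "AEs will be reported according to the IRB defined timelines using appropriate forms". Section 18.2 opens with "Serious Adverse Events are adverse events that" and then lists death, serious deterioration in health (including in-patient hospitalization) and fetal harm.

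Section 18.1 goes on: "All materials and devices used in this study have been approved by local regulatory bodies and are currently on the market". It concludes that no adverse events are to be expected. Section 19 repeats the statement on market status. The abstract in section 1.4 says of the imaging device: "We will utilize SFE laser optical device prototypes", and describes the study as one of its first in vivo dental applications.

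Safety information also appears elsewhere. Table 8.2 has a row "Record of adverse effects", marked at the intervention visit, month 12 and month 24. Section 14.1 sends accidents, incidents and complaints to the IRB as ORIO reports. Table 14.1.2 scores pulpitis in an allocated tooth as a failure. Section 6.3 lists post-operative sensitivity as a secondary endpoint. Section 18.3 names a combined AE/ADE form (Appendix A6).

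**The concern.** A safety record is normally built in two steps: record what happened, then judge whether the study caused it. Here the judgement is part of the definition, so it comes first. An event thought unrelated has no required place in the AE or SAE record, and nobody can later review whether that opinion was right.

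This matters for three reasons. Serious events are filtered in the same way as minor ones. The judgement may be made by someone who knows the allocation, and the same symptom may be attributed more or less readily after acid gel and resin than after varnish. And the section reassures the reader with a statement on device status that does not fit the imaging device, which has had little dental use. Events not recorded at the time may not be recoverable afterwards.

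**Working it through.** No arithmetic applies. The check is a reading of each place that defines, records or reports safety events.

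**1. The AE definition (18.1).** Two conditions must both hold: association with the materials or procedures, and a consequence. The consequence may be unplanned care or a change in risk; either is enough. Association has no alternative.

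**2. The SAE definition (18.2).** It starts from adverse events, so an SAE must first satisfy 18.1. A hospitalization considered unassociated fails at that step, whatever its severity.

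**3. Onward reporting.** IRB reporting in 18.1 applies to AEs and to adverse reactions to treatment. The faster timeline in 18.4 starts from an SAE. The slower one covers other reportable events, a term that the available text does not define.

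**4. Other routes, each tested for whether it gives a full record regardless of cause.**

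| Route | Relatedness condition | What it lacks |
|---|---|---|
| Adverse effects row, Table 8.2 | None stated | No definition of its own; the word for effects is itself causal |
| ORIO reports, 14.1 | None stated | Goes to the IRB; not described as a safety dataset by arm |
| Sensitivity endpoint, 6.3 | None stated | One event type |
| Pulpitis rule, Table 14.1.2 | None stated | One event type, scored as an efficacy failure |
| Patient-level reactions, Table 14.1.2 | Reaction to a study material | Related events only |
| AE/ADE form, 18.3 | Cannot be checked | Appendix A6 is not in the available text |

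Some unrelated events can reach the record by the first four routes. None of the routes that can be read captures all of them.

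**5. Who judges.** No section assigns the association judgement or gives criteria for it. Section 8.2 has the study clinician deliver the allocated treatment, so that person knows the arm. Section 11.4.2, headed as blinding, covers only code numbers and confidentiality.

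**6. Device status and foreseeable events.** The market claim in 18.1 and 19 covers all devices; 1.4 calls the SFE devices prototypes. The expectation of no events in 18.1 stands beside the discussion of resin allergy in 5.2 and the sensitivity endpoint in 6.3.

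**7. Unit of tabulation.** Section 9.3 randomizes lesions, and 6.4 allows two per child in separate quadrants. Nothing in 9.3 keeps both in one arm, so an event affecting the child as a whole may not belong to a single arm.

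**The case against.** The strongest reply is that the protocol does not rely on 18.1 alone. A reader might infer that unrelated events are never captured. The documents do not support that: the routes in 6.3, 8.2, 14.1 and Table 14.1.2 could pick some of them up, and the CRF (Appendix A1) and AE/ADE form cannot be inspected. That part of the objection stands, and it limits the point to what the AE and SAE definitions require.

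Three other stronger readings also fail. An event need not have led to unplanned care, because 18.1 accepts a change in risk instead. No text says that an unmasked clinician decides on association; this is an inference from who gives the treatment. And the halt rules in Table 14.1.2 do not owe their dependence on attribution to 18.1. They count side effects, which require attribution by their own wording, and they would still do so after the change proposed here.

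It is also fair to say that neither section 11.4 nor the SAP plans a comparison of adverse events by arm, so no planned AE test is biased. The post-operative sensitivity comparison does not pass through 18.1 at all. On the SFE, section 5.1 reports safe use in other human applications and a non-significant-risk determination by the FDA. That bears on risk, but it is not market status, so the conflict with 1.4 remains.

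None of this supplies a rule to record AEs and SAEs regardless of cause.

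**Conclusion.** The point holds in this form: the AE definition is conditional on association, the SAE definition inherits the condition, and events considered unrelated, including death or hospitalization, fall outside AE/SAE recording and reporting. This is a stated rule, not a missing detail. Attribution that differs by arm is a risk that follows from an unnamed assessor and a treating clinician who knows the allocation; the documents do not show that it will occur. The statements in 18.1 on device status and expected events are inconsistent with 1.4, 5.2 and 6.3.

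The size cannot be given as a number, because the documents contain no adverse event rate and no rate of attribution. The primary endpoint, lesion progression, is not affected. The conclusion assumes that the unseen appendices do not override the definitions in the body of the protocol. The change should be made, but the point does not by itself put the trial's efficacy result in doubt.

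**What to change.** - **Definition.** Remove the association condition from 18.1. Record, whether or not judged related, every event on the 18.2 seriousness list, and every untoward event that is oral or dental, prompts unplanned care, or alters a child's risk. This keeps everything that 18.1 now covers, including a non-oral reaction to resin, which a restriction to oral and dental events would lose.
- **Relatedness.** Record it in a separate field for each of resin, varnish, spacer and SFE. Name the assessor and state whether that person is masked.
- **Tabulation.** Show tooth-level events by the arm of the lesion. Show patient-level events by the child's allocation: Icon only, control only, or both.
- **Consistency.** Correct the market-status and no-expected-events statements in 18.1, and the repeated market-status statement in section 19, so that they agree with 1.4, 5.2 and 6.3.

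The cost is protocol wording, added CRF fields and some additional event forms. The exact changes to the forms depend on Appendices A1 and A6, which could not be checked. The change alters no treatment and leaves the halt rules as they are.
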